8.5.3 Sample adjustment

Since the relative weight of each country and each category of HCPs in the final sample may be different from its real proportion, the extrapolation of the raw survey results to the overall target population would not be relevant without adjustment. The survey results will be weighted to reflect the real proportion of the countries and the real proportion of each speciality in order to allow the extension of the survey results to the

Alecensa—F. Hoffmann-La Roche Ltd Protocol BO40643, Version 1 overall target population. Both unweighted and weighted results will be presented in the report.

A weight variable will be applied to each statistical unit (i.e., the HCPs) during the results calculation to correct any over-or under-sampling that may have occurred for a country or speciality. This weight variable will indicate how many unit(s) of the population of interest an observation will count in a statistical procedure. Its value will change per country and per speciality. The weights will be normalized to obtain their sum equal to the sample size.

8.6 DATA MANAGEMENT

will be responsible for data management of this study, including quality checking of the data.

The survey will be conducted according to the Standard Operating Procedures (SOPs) of and .

Collected data will be entered and stored in a central database specific to the survey.

A study database will be created by merging the databases of each country together. The study database will be locked once validated.

8.6.1 Data Quality Assurance

QC team will be responsible for the data management of this study, including quality checking of the data. Will produce a Data Quality Review Plan that describes the quality checking to be performed on the data.

Data will be checked in terms of consistency before data analysis:

- Removal of duplicates (if required)
- Data labelling and data formatting
- Range and consistency checks for each variable to identify potential nonadmissible values (implausible answers, e.g., an answer of 999mg)

Automatic checks for plausibility and consistency will be programmed into the questionnaire tool, which will prevent contradicting values from being entered. not query HCPs' answers to questions in the questionnaire.

will

Non-admissible values will be avoided by implementation of the appropriate controls in the questionnaire at the time of its completion by the HCPs. Any non-admissible values identified after database lock (if any) will be excluded from the analysis.

The marketing authorization holder will perform oversight of the data management of this study, including approval of data management plans and specifications.

The QC team will comply with the Roche's procedures regarding archiving and record management.

8.6.2 Source Data Documentation

Not applicable

8.7 DATA ANALYSIS

General considerations

The statistical analysis will be conducted using the SAS software (Version 9.4 or above).

The statistical results of the HCP data will be presented in the same report, by country, by speciality, and in total (see Table 4 as example).

Continuous variables will be presented by their number (of valid cases), mean, standard deviation, and median, Q1, Q3, minimum, and maximum.

Categorical variables will be presented as the total number and relative percentage per category. These will be the percentage per category.

In case of multiple choice questions, the frequency of each option provided by the physicians will be reported in the statistical results. Different combinations of the answers provided will not be considered.

Confidence intervals of 95% will be estimated, as appropriate.

Country	Speciality (Pulmo)	Speciality (Onco)	All (unweighted)	All (weighted)
Country 1	(N=xx)	(N=xx)	(N=xx)	(N=xxx)
answer 1	xx (xx.x%)	xx (xx.x%)	xx (xx.x%)	xx (xx.x%)
answer 2	xx (xx.x%)	xx (xx.x%)	xx (xx.x%)	xx (xx.x%)
answer 3	xx (xx.x%)	xx (xx.x%)	xx (xx.x%)	xx (xx.x%)
Country 2	(N=xx)	(N=xx)	(N=xx)	(N=xx)
answer 1	xx (xx.x%)	xx (xx.x%)	xx (xx.x%)	xx (xx.x%)
answer 2	xx (xx.x%)	xx (xx.x%)	xx (xx.x%)	xx (xx.x%)
answer 3	xx (xx.x%)	xx (xx.x%)	xx (xx.x%)	xx (xx.x%)
Country 3	(N=xx)	(N=xx)	(N=xx)	(N=xx)
answer 1	xx (xx.x%)	xx (xx.x%)	xx (xx.x%)	xx (xx.x%)
answer 2	xx (xx.x%)	xx (xx.x%)	xx (xx.x%)	xx (xx.x%)
answer 3	xx (xx.x%)	xx (xx.x%)	xx (xx.x%)	xx (xx.x%)
Country x	(N=xx)	(N=xx)	(N=xx)	(N=xx)
answer 1	xx (xx.x%)	xx (xx.x%)	xx (xx.x%)	xx (xx.x%)
answer 2	xx (xx.x%)	xx (xx.x%)	xx (xx.x%)	xx (xx.x%)
answer 3	xx (xx.x%)	xx (xx.x%)	xx (xx.x%)	xx (xx.x%)

Table 4 Mock Tables to Implement in the Statistical and Study Reports

Alecensa—F. Hoffmann-La Roche Ltd

Protocol BO40643, Version 1

Overall - unweighted results	(N=xx)	(N=xx)	(N=xx)	(N=xxx)
answer 1	xx (xx.x%)	xx (xx.x%)	xx (xx.x%)	xx (xx.x%)
answer 2	xx (xx.x%)	xx (xx.x%)	xx (xx.x%)	xx (xx.x%)
answer 3	xx (xx.x%)	xx (xx.x%)	xx (xx.x%)	xx (xx.x%)
Overall - weighted results	(N=xx)	(N=xx)	(N=xx)	(N=xxx)
answer 1	xx (xx.x%)	xx (xx.x%)	xx (xx.x%)	xx (xx.x%)
answer 2	xx (xx.x%)	xx (xx.x%)	xx (xx.x%)	xx (xx.x%)

Note: the table structure may be adjusted for the final study report.

Handling of missing data

. . . .

All questions in the questionnaire will be mandatory and cannot be skipped. Questionnaires can only be submitted when fully completed. Therefore, missing data are not expected to occur.

Entering erroneous information is only possible for open questions. These nonadmissible values (if any) identified after database lock will be excluded from analysis.

Analysis of HCP Participation Rate

The following different cases will be distinguished:

- HCPs who refused to participate (R): HCPs explicitly mentioned their refusal to participate
- HCPs with partial questionnaires (P): HCPs who clicked on the link provided in the invitation email, who began the questionnaire but never submitted it
- HCPs with completed questionnaire (C): HCPs who completed the entire questionnaire
- Contacted HCPs: HCPs who was reached by phone or who received a web link to the online survey via email. For survey invitations issued via postal mail the assumption will be made that if mail is not returned, HCP will be considered "contacted" = C+P+R
- HCPs who agreed to participate: HCPs willing to participate in the survey (e.g., by phone or by clicking on the link provided in the invitation email) = P+C

The HCPs' participation in the survey will be examined as follows (adapted from: *American Association for Public Opinion Research 2016*):

- Response rate = $\frac{C}{C+P+R}$
- Refusal rate = $\frac{R}{C+P+R}$

The participation rates will be presented by country and by speciality.

Questionnaire analysis

Analysable questionnaires are those completed and submitted by the participants on the web or by phone. If the questionnaire is just filled on the web but not submitted, or if the name and surname of the participant is disclosed, the questionnaire will not be analysed and will be discarded.

The proportions of correct and appropriate answers to selected questions asked in the questionnaire will be expressed among HCPs who provided answers to those questions.

Awareness questions (Questions Q2 to Q3 of HCP questionnaire: Individual HCP awareness scores will be descriptively analysed and reported as percentages. HCP awareness level will be calculated as the mean of the individual scores.

Knowledge questions (Questions Q5 to Q8 of HCP questionnaire): For each question, the number and percentage of HCPs answering correctly each subquestion will be presented. Subsequently, individual HCP knowledge scores will be calculated as the percentage of correctly answered knowledge questions; scores will range from 0 to 100% with 100% representing the percentage of all knowledge questions being answered correctly. HCP knowledge level will be calculated as the mean of individual scores.

Clinical practice questions (Questions Q9 and Q10 of HCP questionnaire): For each question, HCPs answering correctly each sub-question will be presented. Subsequently, individual HCP clinical practice scores will be calculated as the percentage of correctly answered survey questions; scores will range from 0 to 100% with 100% representing the percentage of all clinical practice questions being answered correctly. HCP clinical practice level will be calculated as the mean of individual scores.

In a first step, calculations will be performed on raw data. No projection factor will be applied to generalize the results to the entire prescribers' universe. As a consequence, the line "Overall - unweighted results" will show only the results observed on the overall sample and will not reflect the countries' universe since this sample is not proportional to the size of the lists in each country.

In a second step, the results will be weighted according to the real proportion of HCPs in each country in order to accurately reflect the population that the survey seeks to measure.

Possible selection bias will be assessed by comparing the distributions of available characteristics (e.g., country, type of setting (hospital or office-based), and speciality, if applicable and feasible) between respondent and non-respondent HCPs.

Moreover, the profile of HCPs with incorrect answers could be identified and described with all available relevant covariates collected in the survey (e.g., country, duration of practice, type of setting, and speciality) and past experience with Alecensa (number of patients treated).

Assessment of success

A successful outcome on the effectiveness of risk minimisation measures is defined a priori by the following target levels:

- Proportion of HCPs being aware of the important identified risk and related minimisation measures for Alecensa (Question Q2 and Q3 of HCP questionnaire) – Success: ≥75%
- 2. Proportion of HCPs knowledgeable about the important risks, specific monitoring, dose modification (Questions Q5 to Q8 of HCP questionnaire) Success ≥60%
- 3. Proportion of HCPs answering the clinical practice questions in compliance to the SPC (Questions Q9 andQ10 of HCP questionnaire) Success ≥75%

The proportion of HCPs meeting the success criteria in all three categories is the overall success factor for the implementation of RMM for the important identified risks for Alecensa. The thresholds used are in accordance with success rates applied in other studies approved by PRAC and provide a balance between the ideal scenario of achieving a 100% rate of awareness, knowledge and compliance and what can be realistically expected from routine RMMs in the clinical practice.

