8.3 VARIABLES

The following variables will be considered:

1) Variables related to HCPs participation:

The following different cases will be distinguished (for details see definition in 8.7 Data Analysis):

- Response rate
- Refusal rate
- 2) Variables related to HCPs practice information:
 - Location (country)
 - Duration of practice (years of practice as a physician)
 - HCP primary speciality (oncologist, pulmonologist)
 - Type of setting (office-based, hospital based or both)
 - Past experience with Alecensa (number of patients treated)

- 3) Variables related to the HCP awareness about the important identified risks in the label of Alecensa as well as the HCP awareness of clinical measures with respect to the identified risks (W&P) percentages of HCPs with the answer "yes":
 - Awareness of important identified risks (yes/no)
 - Awareness of clinical measures for risk minimization (yes/no)
- 4) Variables related to the HCPs knowledge on the requirement for specific monitoring and dose modification percentages of HCPs with correct answers:
 - Important identified risks (W&P) for Alecensa (tick boxes with correct and false answers)
 - Specific monitoring with respect to the important identified risks (W&P) (tick boxes with correct and false answers)
 - Specific advice to patients with respect to the important identified risks (W&P) (tick boxes with correct and false answers)
 - Requirements for terminating Alecensa or specific dose modifications for the important identified risks (W&P) (tick boxes with different instructions for the management of patients, one correct answer possible per scenario)
- 5) Variables related to the HCPs clinical practice with respect to compliance with the clinical measures for important identified risks (W&P) percentages of HCPs with correct answers:
 - Frequency of monitoring measures (tick boxes with correct and false answers) including:
 - o AST/ALT monitoring
 - Creatine Phosphokinase (CPK) monitoring
 - o Heart rate and blood pressure monitoring
 - Dose reduction scheme (to be filled in by the HCP)
- 6) Other variables: Source of information for Alecensa safety profile and prescribing information percentages of HCPs per source of information

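### Non-admissible write-in answers found after database lock are excluded rather than scored as incorrect, which can only raise the proportion correct on the dose-reduction item

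*Protocol*

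**What the plan says.** - **The rule.** Under the missing-data heading of section 8.7 the protocol states: "Entering erroneous information is only possible for open questions. These nonadmissible values (if any) identified after database lock will be excluded from analysis". Section 8.6.1 has the same rule: "Any non-admissible values identified after database lock (if any) will be excluded from the analysis". Neither place says that such an entry is scored as incorrect.
- **What counts as non-admissible.** Section 8.6.1 describes "potential nonadmissible values (implausible answers, e.g., an answer of 999mg". The example is a dose.
- **Where a dose is written in.** Section 8.3, item 5, lists among the clinical practice variables "Dose reduction scheme (to be filled in by the HCP". The other variables in that item, the monitoring frequencies, are tick boxes. All of item 5 is to be reported as percentages of HCPs with correct answers.
- **The denominator.** Section 8.7 says that proportions of correct answers "will be expressed among HCPs who provided answers to those questions".
- **The score and the target.** Section 8.7 defines the individual practice score as the percentage of practice questions answered correctly, with 100% meaning that every one of them is right. The practice target is at least 75%, over Q9 and Q10 together, and it feeds the overall success factor.
- **Safeguards.** Section 8.6.1 plans plausibility controls in the entry tool and range checks before analysis. It also says that respondents' answers will not be queried.

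**The concern.** The survey is meant to find out whether prescribers apply the label guidance correctly. For a scored dose item, an impossible dose cannot be a correct answer. Removing it because it is impossible makes membership of the analysis set depend on the outcome, and always in the same direction: an entry that could only have counted against success disappears. The results are uneven as well. A near miss counts against the HCP, whereas a dose far outside any plausible range does not.

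At stake are the proportion correct on the dose-reduction item and, depending on how the score is computed, the practice level judged against 75%.

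**Working it through.** **Inputs from the protocol.** Planned sample 200 and assumed P of 50% (8.5.1); practice target 75% (8.7); practice variables consisting of three monitoring frequencies (AST/ALT, CPK, heart rate with blood pressure) and the dose reduction scheme (8.3, item 5).

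**Assumptions, not in the protocol.** The share of HCPs with a non-admissible entry that survives to the locked database, *x*, is taken as 1% to 5%. The number of equally weighted practice items, *m*, is taken as 4, following the list in 8.3. The average on an affected HCP's other items, *a*, is taken as 75%.

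**Step 1: the plan's own precision figure.** Half-width = 1.96 × √(0.5 × 0.5 / 200) = 6.93%, against the stated ±6.9%. It reproduces.

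**Step 2: item level.** Let *p* be the share correct when all HCPs are scored. If a share *x* is wrong and excluded, the reported proportion is *p* / (1 − *x*), which is never below *p*. Illustration with 144 of 200 correct (72.0%):

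| Excluded | Reported proportion |
|---|---|
| 0 | 144/200 = 72.0% |
| 2 (1%) | 144/198 = 72.7% |
| 4 (2%) | 144/196 = 73.5% |
| 10 (5%) | 144/190 = 75.8% |

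These are proportions for one item. The 75% target applies to Q9 and Q10 together, so the last row does not show the criterion being crossed.

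**Step 3: score level, item dropped from the HCP's own denominator.** Scored as wrong, an affected HCP averages *a*(*m* − 1)/*m* = 75 × 3/4 = 56.25%. With the item dropped, the average is 75%. The gain per affected HCP is *a*/*m* = 18.75 points, and the mean score moves by *x* × 18.75:

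- 1% affected: 0.19 points
- 2% affected: 0.38 points
- 5% affected: 0.94 points

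**Step 4: sensitivity to the number of items.** The gain per affected HCP is 75/2 = 37.5 points with two items and 75/6 = 12.5 points with six. At 1% affected the shift is then 0.13 to 0.38 points, and at 5% it is 0.63 to 1.88 points.

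**Step 5: score level, fixed denominator.** If the score always divides by the full number of practice questions, an excluded entry simply fails to count as correct. The affected HCP keeps 56.25%, and the shift in the mean score is zero. The item-level effect in step 2 remains if its denominator is HCPs with a retained answer.

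**The case against.** **Scope.** The rule is narrow. It reaches only non-admissible values that have passed the entry controls and the pre-analysis checks and are found after lock. A reader might infer from "Entering erroneous information is only possible for open questions", followed directly by the exclusion, that every wrong write-in answer is dropped. The documents do not support that: the operative sentence concerns non-admissible values, which 8.6.1 describes as implausible ones. A plausible but wrong dose, likely the usual form of a practice gap, is still scored wrong. This part of the objection stands.

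**Denominator.** The score definition in 8.7 can be read as dividing by the full set of practice questions, in which case the score is not inflated (step 5). One can also argue that an HCP who typed 999 mg did answer the question. So the effect on the score is conditional. Still, excluding a value from the analysis and then counting its author among those who answered is a strained reading, and at item level the plain sense is that the entry leaves the denominator.

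**Slips.** An entry of this kind may be a typing error or a filler in a mandatory field. Because answers are not queried, slips cannot be told from wrong beliefs, and scoring all of them as wrong may slightly understate practice. That stands, and it is a reason for showing both results.

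**Left to other documents.** Scoring detail may sit in the SAP or the Data Quality Review Plan, neither of which is at hand. But the protocol is not silent here. It fixes exclusion in two places, and a later document that scored these entries as incorrect would depart from it.

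**Missing data.** The remark that missing data are not expected does not contradict the rule. It states an expectation, followed by a fallback for values that occur, if any.

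**Conclusion.** The point holds in a limited form. For a scored write-in item, the stated rule removes answers that cannot be correct, and on the plain reading of the denominator it can only raise the proportion correct on that item. The mean practice score rises as well unless its denominator is fixed at all practice questions, which the protocol does not settle.

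The size is unknown and probably small. Under the assumptions of step 3, the mean score rises by about 0.2 to 0.9 points for 1% to 5% of HCPs affected, well inside the planned ±6.9%. Unlike sampling error, however, the shift goes one way and does not shrink with a larger sample. The questionnaire items are not shown, so the place of the write-in item within Q9 and Q10 rests on its listing under clinical practice in 8.3.

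A reader might infer that the rule by itself would carry the practice domain past its target. The documents do not support this. They give no rate of non-admissible entries, the entry controls point to a low one, and the target does not apply to the dose item alone. Severity: minor to moderate.

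**What to change.** In sections 8.6.1 and 8.7:

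- State that a non-admissible entry in a scored item (the dose reduction scheme) counts as an incorrect answer, and that both the HCP and the item stay in the denominator, whether the entry is found before or after lock.
- Limit exclusion to open fields that are not scored.
- State that the individual practice score always divides by the full number of practice questions.
- Report the number of non-admissible entries, and show the result with exclusion as a sensitivity analysis, because slips and wrong beliefs cannot be separated.

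The cost is a sentence or two in each section and one extra table line. The practice result may come out slightly less favourable, and a few typing slips would count as wrong; the sensitivity analysis shows how much this matters.

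### Implausible answers to the scored open dose item are excluded from analysis rather than counted as incorrect, which can only leave the percent correct unchanged or raise it

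*Protocol*

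**What the plan says.** Section 8.7, Handling of missing data, explains that all questions are mandatory and then adds: "Entering erroneous information is only possible for open questions". The next sentence is the rule at issue: "These nonadmissible values (if any) identified after database lock will be excluded from analysis". Section 8.6.1 states it a second time: "Any non-admissible values identified after database lock (if any) will be excluded from the analysis". It describes non-admissible values as "implausible answers, e.g., an answer of 999mg" and expects few of them: "Non-admissible values will be avoided by implementation of the appropriate controls in the questionnaire at the time of its completion by the HCPs".

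Section 8.3 lists the clinical practice variables, which are reported as percentages of respondents answering correctly. There are three monitoring-frequency items with tick boxes (AST/ALT, CPK, heart rate and blood pressure) and one fill-in item: "Dose reduction scheme (to be filled in by the HCP".

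Section 8.7, Questionnaire analysis, says that proportions correct "will be expressed among HCPs who provided answers to those questions". It defines each respondent's practice score as the percentage of practice questions (Q9 and Q10) answered correctly, and the practice level as the mean of those scores. Assessment of success sets a target of at least 75% for clinical practice. Nothing in the protocol says that an implausible entry is scored as incorrect.

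**The concern.** The survey measures whether prescribers know and apply the label guidance. On a scored fill-in item, an implausible dose is a failure on the outcome being measured. The plan treats it as if it were missing. Every answer the rule removes from this item would otherwise have scored zero, so any effect on the item's percent correct favours a finding that the risk minimisation measures work.

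Clinical practice is one of the three categories that make up the overall success factor. The admissible range is not stated and the exclusion is made after database lock, so some discretion remains over one component of a success criterion.

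**Working it through.** **Inputs.** From the protocol: 200 completed questionnaires (8.5.1), the 75% practice target (8.7), one open item among the practice variables (8.3), and a practice level defined as the mean of individual scores (8.7). Not in the protocol, so assumed: the number of non-admissible entries, and the number and weight of practice items. The questionnaire itself is not shown.

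**The plan's own figure.** The 95% half-width at P = 50% and n = 200 is 1.96 × √(0.25/200) = 6.93%, which agrees with the stated ±6.9%.

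**1. The dose item alone.** Let C be the number correct and x the number of non-admissible entries. Counted as incorrect, the result is C/200 whatever x is. Excluded, it is C/(200 − x).

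| C/200 | x = 1 | x = 2 | x = 3 | x = 5 | x = 10 |
|---|---|---|---|---|---|
| 148/200 = 74.0% | 74.4% | 74.7% | 75.1% | 75.9% | 77.9% |
| 140/200 = 70.0% | 70.4% | 70.7% | 71.1% | 71.8% | 73.7% |

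From 74.0%, three exclusions (1.5% of respondents) are enough to pass 75%: 148/197 = 75.1%. From 70.0% it takes 14 (7%): 140/186 = 75.3%.

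**2. The mean of individual scores.** Take m equally weighted items, one of them open, and let q be an affected respondent's proportion correct on the other m − 1 items.
- Open item kept as incorrect: score = (m − 1)q/m.
- Open item dropped: score = q.
- Gain for that respondent: q − (m − 1)q/m = q/m, at most 1/m.
- Gain in the mean when a share k is affected: kq/m, at most k/m.

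| k | Upper bound, m = 2 | Upper bound, m = 4 |
|---|---|---|
| 1% | 0.5 points | 0.25 points |
| 5% | 2.5 points | 1.25 points |
| 10% | 5.0 points | 2.5 points |

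With q between 0.75 and 0.85 and k = 5%, the gain is 1.9 to 2.1 points for m = 2 and 0.9 to 1.1 points for m = 4.

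Three affected respondents (k = 1.5%) add at most 0.75 points with two items or 0.375 with four. A mean of 74.0% would therefore reach at most 74.75% or about 74.4%, short of 75%.

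**3. Fixed denominator.** If the excluded value earns no credit but its question still counts in the respondent's denominator, the score remains (m − 1)q/m and the gain is zero.

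**The case against.** A reader might infer that a handful of exclusions could turn a failed practice result into a pass. The documents do not support that. The crossing in step 1 treats practice as one yes/no item, whereas 8.7 defines a mean over several questions. On that scale, with two or four items, neither the 74% case with 1.5% affected nor the 70% case with 7% affected reaches 75%: the upper bounds for the latter are 73.5% and 71.75%. Nor is removal from the denominator certain. The text excludes values, and the stated grounds for discarding a questionnaire do not include an implausible value. A respondent who typed an implausible dose did provide an answer, and a score in which 100% means all practice questions correct is compatible with a fixed denominator. These points stand, and they limit the size.

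A reader might also infer that the live entry controls inflate the score by prompting corrections. Section 8.6.1 describes checks for plausibility and contradiction, not for agreement with the SPC. A plausible but wrong dose is still accepted, and rejecting an absurd number does not reveal the right one. Removing range checks would also let more keying errors into a scored item, so that is a trade-off and not a defect. The knowledge questions are not exposed either, because 8.3 describes those variables as tick boxes. Finally, 75% is a target level and no hypothesis test is specified.

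Some implausible entries will be keying slips by people who know the answer. That is a real cost of scoring them as incorrect, but it does not justify treating every implausible dose as missing.

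**Conclusion.** The point holds as a flaw in a rule the protocol states twice. It is not detail left to a later plan. Excluding implausible entries from the scored dose item can leave its percent correct unchanged or raise it, but cannot lower it.

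The effect is probably small, since entry controls should leave few such values and the protocol gives no count. On the single item with 200 respondents, three exclusions move 74.0% to 75.1%. On the mean-score scale the rise is at most k/m, and it is nil with a fixed denominator. It could matter to the practice target only if the result falls just below 75%.

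This rests on three assumptions: that the dose scheme is scored within Q9 and Q10, as 8.3 and 8.7 together imply; that items are equally weighted; and that the exclusion acts on the value or item and not on the whole respondent.

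**What to change.** In 8.6.1 and 8.7, state that a non-admissible entry to a scored open question is counted as incorrect, with both the respondent and the item kept in the denominator. Report the number of such entries, and present the result with them excluded only as a sensitivity analysis. Keep the exclusion rule for unscored descriptive variables such as years of practice. The live checks can stay as they are.

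The cost is a sentence or two in each section. A few keying errors will be scored as incorrect and the reported rate may be slightly lower; the sensitivity analysis will show by how much.
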